## 2.1. Outcome Measures

- The primary outcome measure of the study will be greater improvement in calcinosis activity VAS rating from Week 0 to Week 10, compared with any change in calcinosis activity VAS rating observed during the pre-treatment period (from Week -10 to Week 0).

Secondary outcome measures include:

- Greater improvement in quality of life score (CHQ-PF50 for children, SF-36 for adults) from Week 0 to Week 10, compared with any change in quality of life score observed during the pre-treatment period (from Week -10 to Week 0).
- Changes in components of quality of life over time, as measured by quality of life questionnaires (e.g., SF-36, CHQ-PF50, PROMIS, Skindex-29)
- Changes in functional disability over time, measured by CHAQ/HAQ, CMAS/AMAT/Myositis Functional Index, and physical therapy-related assessments (e.g., range of motion, 6-minute walk, timed up and go, sit to stand, Motor Functional Measure (MFM))
- Change in muscle strength over time, measured by manual and quantitative muscle testing

**Abbreviated Title:** Sodium Thiosulfate (STIC)

**Version Date:** July 07, 2023

- Improvement of calcinosis lesions, assessed by Calcinosis Assessment Tool, Sentinel Calcinosis Lesion form, Mawdsley Calcinosis Questionnaire, durometry measurements, photography, and imaging studies
- Changes in gene expression, measured by RNA and protein analyses (e.g., to evaluate changes due to therapy, or differences between responders and non-responders to therapy)
- Incidence and severity of adverse events, including laboratory abnormalities, over time
- Improvement in or stabilization of myositis activity and damage, as assessed by the IMACS core set measures

Secondary outcomes will evaluate for differences in change from week -10 to 0 compared to week 0 to 10 as well as changes at week 24 and 62.

An additional outcome will be validation of the Calcinosis Assessment Tool and the Mawdsley Calcinosis Questionnaire and new imaging modalities for calcinosis, which are under development by our group and associate investigators of the protocol.

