- **Week -10 (Enrollment/Intake):** Participants will come to the NIH Clinical Center for an initial evaluation to confirm qualification for the study and to conduct baseline evaluations. Study participants (or their parent(s)/guardian(s)) must sign a consent form, and minors must provide assent before they can be enrolled in the study and before any study assessments are performed. Any participants who are diagnosed with a medical condition or have laboratory abnormalities that were previously unknown will be notified and referred for medical care. For example, if a participant is found to be vitamin D deficient their physician will be notified and they can replace based on Institute of Medicine or National Osteoporosis Foundation guidelines. The Week -10 visit is expected to last up to approximately 7 days and may be done on either an inpatient or outpatient basis depending on the needs and mobility of the participant. Participants who have equivalent laboratory evaluations, imaging studies, or physical assessments within 1 week of their -10 visit may have those results used for this protocol instead of repeating those tests under this protocol.
- **Week -4:** Participants will complete questionnaires only (Calcinosis Assessment Tool, Mawdsley Calcinosis Questionnaire, Quality of Life, and patient-reported assessment measures); this may be done at the participant's home or at NIH.

**Abbreviated Title:** Sodium Thiosulfate (STIC)

**Version Date:** July 07, 2023

- **Week 0 (Baseline):** Eligible participants will return to the NIH approximately 10 weeks following the Week -10 visit for a second evaluation, during which time they will be admitted to the NIH Clinical Center as an inpatient and will initiate IV sodium thiosulfate (STS) therapy, dosed at 16 g/m^2 three times weekly for 10 weeks. Female individuals of reproductive potential must have a negative urine or serum pregnancy test prior to administration of sodium thiosulfate. Any participants experiencing intolerable side effects may discontinue therapy earlier. Participants who tolerate the therapy without an adverse event for 2 infusions and are deemed by the medical staff to be medically stable will be given the choice of becoming local outpatients to the NIH Clinical Center and returning 3 times weekly for infusions and evaluations during the 10-week sodium thiosulfate treatment period. Safety monitoring will be performed throughout the treatment period (see Table 8).

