Two-sided paired t-tests will be performed to test for significant differences in the relative percent change in VAS score, absolute percent change in VAS score, and the secondary outcome of change in quality of life score (Physical Function Score of CHQ-PF50 for children, SF-36 for adults) from Week 0 to Week 10, compared with any change in quality of life score observed during the pre-treatment period (from Week -10 to Week 0). The secondary outcomes of changes in the components of quality of life over time, changes in functional disability over time, change in muscle strength over time, and changes in gene expression associated with therapy will also be analyzed using paired t-tests. For the gene expression analysis, multiple testing adjustments will be used to control the false discovery rate. Categorical measures of improvement in calcinosis lesions, improvement in or stabilization of myositis activity, and incidence of adverse events will be analyzed using McNemar tests. Fisher exact tests will be used to test for differences between responders and non-responders to therapy. The severity of adverse events and quantitative measures of improvement in calcinosis lesions and myositis activity will be analyzed using paired t-test or regression to control for additional covariates. Generalized linear mixed models will be considered to analyze quantitative secondary outcomes across time. Descriptive statistics, such as mean, median and standard deviation, of the primary outcome and secondary outcomes of change in VAS, change in quality of life (QOL), change in functional disability, improvement in calcinosis lesions, and change in muscle strength are also of interest and will be used to plan further studies. Prior to statistical testing, the normality of quantitative measures will be evaluated by plotting the empirical distributions of the quantitative measures to look for deviations from normality as well as using QQ-plots. For non-normally distributed endpoints, normalizing transformations, such as the log transformation, will be applied. If normality cannot be achieved by transforming the data, analogous nonparametric tests, such as the Wilcoxon Signed Rank test, will be used in the analysis. The multiple comparison adjustment method that will be used is a stepwise Bonferroni-Class Method as published in Holm (39) and Hochberg (40).

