## **14.2. Subject Monitoring**

Tests used to monitor participant safety are described in Section 14.3 below.

Throughout the treatment period, inpatient participants will be monitored daily while in the clinical center and participants who elect to stay locally and come to the NIH for treatments will be monitored 3 times weekly. Additional visits occurring approximately 14 weeks and 52 weeks after the treatment period ends will allow for an assessment of any delayed safety or efficacy issues. Any new medical issues that arise during treatment will be addressed and managed.

Criteria for individual participant withdrawal from the treatment phase of the study include:

- Inability to comply with the requirements of the protocol (including inability to tolerate the sodium thiosulfate therapy)
- Breastfeeding or pregnancy detected prior to Week 10
- Serious adverse event necessitating discontinuation of the sodium thiosulfate therapy.
- Common Terminology Criteria for Adverse Events level 3 or greater event thought to be related to study drug, besides nausea, prior to week 10.
- Nausea that cannot be controlled by slowing rate of infusion and adding anti-emetic medications prior to week 10.

**Abbreviated Title:** Sodium Thiosulfate (STIC)

**Version Date:** July 07, 2023

- A new fracture prior to week 10. If a patient develops a fracture prior to week 0 if the patient would meet enrollment criteria in a year or greater time they may have a second -10 visit and continue from there with the normal study process.
- Patient request to withdraw from the study.
- Patients who have new medical problems develop during the study not thought to be related to study drug will be treated per standard of care medicine. If it is felt that the new condition makes it unsafe for the patient to continue in the study, then they will be withdrawn.
- Withdrawn patients will continue to be followed according to the schedule of the protocol and return for all assessment visits as tolerated and safe.

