## Appendix B. Time and Events Tables

**Table 4 Overview of Study Procedures Performed by Study Week**

	Pre-treatment			Treatment											Follow-up	
	Screening	Week												24	62	
		-10	-4	0	1	2	3	4	5	6	7	8	9			
Inclusion/exclusion criteria assessment	X	X														
Sodium thiosulfate treatment (3x/week) a,b					X	X	X	X	X	X	X	X	X			
Check for rapid responder and termination of treatment											X					
Medical history	X	X		X		X				X	X			X	X	X
Medication history and concomitant medications c	X	X		X		X				X				X	X	X
Review of systems every 2 weeks during infusion		X		X		X		X		X		X		X	X	X
Physical exam	X	X		X		X		X		X		X		X	X	X
Pregnancy test for women of child-bearing potential	X	X		X	X	X	X	X	X	X	X	X	X	X	X	X
Myositis clinical activity and damage assessments (Table 7)	X	X		X		X		X		X		X		X	X	X
Muscle function and strength testing (see Table 7 for details)	X	X		X		X		X		X		X		X	X	X
Skin Assessments (see Table 7 for details)	X	X		X		X		X		X		X		X	X	X
MRI (whole body)		X								X					X	X p
CT scan without contrast (all extremities)				X											X	X
CT scan without contrast (trunk)				X											X	X
MRI/PET				X q										X n,q		X m,q
Infrared photography		X		X		X				X				X	X	X
Nailfold capillaroscopy		X		X		X				X				X	X	X
Photography d		X		X						X				X	X	X
Laser Speckle Contrast Imaging	X		X		X					X				X	X	X

**Abbreviated Title:** Sodium Thiosulfate (STIC)

**Version Date:** July 07, 2023

	Pre-treatment				Treatment										Follow-up	
	Screening	Week														
		-10	-4	0	1	2	3	4	5	6	7	8	9	10	24	62
DEXA for safety monitoring and calcium scoring e	X o	X		X						X				X	X	X
Renal ultrasound		X		X l						X				X l	X	X l
Iothalamate clearance		X f		X						X				X	X g	X g
24-hour urine h		X		X						X				X	X	X
Blood collection (see Table 5 and Table 6 for details) i	X o	X		X	X	X	X	X	X	X	X	X	X	X	X	X
Calcinosis aspiration (as required, and if <15 cc)										X				X	X	X
Calcinosis aspiration (major)														X	X	X
Adverse event monitoring j		X	X	X	X	X	X	X	X	X	X	X	X	X	X	X
Questionnaire completion (see Table 7 below for details)	X	X	X	X		X		X		X		X		X	X	X
IV access k		X		X	X	X	X	X	X	X	X	X	X	X	X	X
Durometry		X		X						X				X	X	X

a. Subjects will receive once-weekly assessments between study weeks 0 and 10

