b. Sodium thiosulfate treatments are administered 3 times/week, starting at Week 0 and continuing through Week 10

c. At Week -10, Week 0, Week 24, and Week 62, medication history and concomitant medications will be reviewed with the subject in detail; at all other visits, any changes occurring since the last evaluation will be assessed.

d. Photography will be performed more frequently than indicated if there's a noted change

e. If a DEXA scan has been performed within 6 months prior to initiation of the study, that will be used as the baseline DEXA evaluation

f. Iothalamate clearance not performed for children at Week -10 visit

g. Iothalamate clearance is optional at Week 24 and Week 62 if normal previously

h. Urine assessment will include calcium, phosphorus, pyrophosphate, creatinine, citrate, and urate; while receiving sodium thiosulfate infusions, evaluations for renal function and urinary excretion of calcium will be performed weekly. They will use a split collection with Cr, Na, CA, Mg, P, and urate coming from the non-acidified container. Cr, citrate, and oxalate will be collected from the acidified container.

i. While receiving sodium thiosulfate infusions, evaluations for renal function, metabolic acidosis, PT/PTT, and serum calcium will be performed weekly

**Abbreviated Title:** Sodium Thiosulfate (STIC)

**Version Date:** July 07, 2023

	Pre-treatment				Treatment										Follow-up	
	Week															
	Screening	-10	-4	0	1	2	3	4	5	6	7	8	9	10	24	62
j.	These are the times for formal review for adverse events. In addition, patients, will have contact information to reach the study team to contact them for any expected adverse events they experience at other times.															
k.	If needed, a PICC or Port-A-Cath line will be inserted to maintain IV access for multiple infusions and this may occur prior to a scheduled visit.															
l.	Only performed if the CT scan during that visit does not include the kidneys.															
m.	If a patient has become pregnant or is breastfeeding and is unable to receive a MRI/PET at this visit they will instead receive a whole body MRI.															
n.	At week 10 adults patients will receive a MRI/PET while pediatric patients will receive a whole body MRI instead.															
o.	May be performed by their home physician															
p.	If the MRI/PET is not performed at this point a whole body MRI if safe will be performed instead.															

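### The McNemar test on adverse-event incidence compares a lead-in with two formal reviews against a treatment period reviewed weekly or more often, so a significant increase could not be attributed to the drug.

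*Combined protocol and SAP*

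**What the plan says.** Section 2.1 lists as a secondary outcome "Incidence and severity of adverse events, including laboratory abnormalities, over time". It adds that "Secondary outcomes will evaluate for differences in change from week -10 to 0 compared to week 0 to 10", together with changes at Weeks 24 and 62. Section 8.1 states that "incidence of adverse events will be analyzed using McNemar tests". That sentence does not name the periods compared, or say whether the test is exact or asymptotic.

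On severity, Section 8.1 says: "The severity of adverse events and quantitative measures of improvement in calcinosis lesions and myositis activity will be analyzed using paired t-test". The sentence goes on to allow regression with covariates, and the section names the Wilcoxon signed-rank test as a fallback when normality cannot be achieved. It gives no severity value for a patient without an event.

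The row "Adverse event monitoring" in Table 4 is marked at Weeks -10, -4 and 0, at every week from 1 to 10, and at Weeks 24 and 62. Note j says: "These are the times for formal review for adverse events". Of the Week -4 contact, Section 3.1 says: "Participants will complete questionnaires only"; this may be done at home. On treatment, Section 14.2 says that "inpatient participants will be monitored daily while in the clinical center", and that local outpatients are monitored three times weekly.

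The chemistry panel is scheduled at Weeks -10 and 0 before treatment. On treatment, note d puts it twice weekly in adults (Table 5), and weekly with two draws in Weeks 6 and 10 in children (Table 6).

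**The concern.** The lead-in is the only comparator in this single-arm trial. A McNemar test compares the proportion of patients with an event in each period. If one period is examined far more closely, that proportion rises there even when the true event rate is unchanged.

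Section 4.1 recognises this for disease flares: it expects them to be noticed more often on treatment because monitoring is closer, and sets a prednisone rule in response. Section 8.1 has no counterpart for adverse events.

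Safety of 10-week use is a secondary objective. A significant p-value from this test could be published as evidence of harm when it partly or wholly reflects surveillance.

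**Working it through.** **The plan's own figures.** No sample size or power is given for the adverse-event test. The trial's size comes from the primary paired t-test. With SD 10 mm, difference 10 mm and two-sided alpha 0.05, 13 patients give 91.1% power. Enrolment is 13 / (1 - 0.25) = 17.3, rounded up to 18. Both figures reproduce, so n = 13 and n = 18 are used below.

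**Looks after intake.**
- Formal reviews: Weeks -4 and 0 = 2, against Weeks 1 to 10 = 10. Contacts on treatment are more frequent still: 3 x 10 = 30 for local outpatients.
- Chemistry: Week 0 = 1, against 2 x 10 = 20 in adults (Table 5) and 8 + (2 x 2) = 12 in children (Table 6). Table 8 gives electrolytes and blood gas once per week, which would be 10. The two schedules need reconciling, but the conclusion is the same under either.

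**Model A, no recall.** Let q be the chance that one look finds an event, the same in both periods (no drug effect). The documents give no such rate, so q is an assumption and is varied. A patient counts as having an event with probability p = 1 - (1 - q)^k for k looks.

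At q = 0.05:
- lead-in 1 - 0.95^2 = 0.10; treatment 1 - 0.95^10 = 0.40;
- discordant toward harm 0.9025 x 0.4013 = 0.362; discordant the other way 0.0975 x 0.5987 = 0.058.

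The exact two-sided McNemar test rejects at 6 discordant patients to 0 (p = 2 x 0.5^6 = 0.031) or 8 to 1 (p = 0.039), but not at 5 to 0 (p = 0.0625). Summing the multinomial probabilities of all significant results in the direction of harm gives:

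| Looks (lead-in vs treatment) | n | q = 0.02 | 0.05 | 0.10 | 0.20 |
|---|---|---|---|---|---|
| 2 vs 10 | 13 | 1.3% | 19% | 48% | 67% |
| 2 vs 10 | 18 | 5% | 38% | 70% | 87% |
| 1 vs 10 (chemistry, weekly) | 13 | 2% | 29% | 71% | 92% |
| 1 vs 20 (chemistry, twice weekly) | 13 | 20% | 83% | 98% | >99% |

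The 1 versus 20 row treats all 13 patients as adults. With 2 versus 2 looks, the false harm rate is at most 0.8% (n = 13) or 1.1% (n = 18) for q from 0.02 to 0.30. The excess therefore comes from the number of looks. The exact test is the cautious choice here: an uncorrected chi-square version would already reject at 4 to 0 (p = 0.046).

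**Model A with q varying between patients** (beta distribution, a + b = 5), 2 versus 10 looks: 2%, 14% and 35% at mean q of 0.05, 0.10 and 0.20 (n = 13); 8%, 35% and 62% (n = 18).

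**Model B, with recall.** Assume 0.1 events per week in both periods and full capture on treatment: p = 1 - exp(-10 x 0.1) = 0.63. Lead-in capture of 75%, 50% and 25% gives p = 0.53, 0.39 and 0.22. The false harm rate is 3%, 11% and 37% (n = 13), or 4.5%, 18% and 57% (n = 18).

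**Period length.** Section 3.1 lets Week 0 move by 32 days either way, so the lead-in can run from 70 - 32 = 38 to 70 + 32 = 102 days. Exposure time can therefore differ as well.

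**The case against.** The strongest reply is that patients are asked at each contact about any events they have had (Section 14.3), so Weeks -4 and 0 can cover the weeks before them. Note j to Table 4 also lets patients report between reviews. Both points stand, and Model B shows that good recall makes the problem small. Neither helps with a transient laboratory abnormality that nobody measured.

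The McNemar sentence names no periods. The pairing is read from Section 2.1; it is the natural reading but should be stated. Weekly contact also does not hold for rapid responders, who have no assessments in Weeks 7 to 9 (Section 3.1).

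Stronger readings are tempting but unsupported:
- **That no result of this test could be interpreted.** The bias runs toward harm, so it would not explain a finding of no increase. What cannot be done is to attribute a significant increase to the drug.
- **That McNemar's test assumes equal detection.** It tests equality of two paired proportions. The fault is unequal measurement, which would affect any test comparing these periods.
- **That severity will be analysed only by paired t-test.** Section 8.1 also allows regression and has the signed-rank fallback. The gap is the undefined score for patients without an event.
- **That safety decisions depend on this p-value.** Safety board review, withdrawal criteria and the pause after three serious events (Sections 14.1, 14.2 and 14.4) do not use it.

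**Conclusion.** The concern holds as a bias toward harm in one secondary safety comparison. The unequal schedule is plain in the documents. The size of the effect is not, because it rests on assumed detection rates.

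With 13 patients and 2 versus 10 independent looks, the chance of a false harm signal runs from about 1% at a 2% per-look rate to 67% at 20%. It is lower if rates vary between patients or if recall is good, and higher with 18 patients. For adult chemistry at 1 versus 20 looks, it is 20% even at a 2% rate. A true drug effect may also exist; this test cannot separate it from closer monitoring. The change is a cheap improvement and should be made.

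**What to change.** 1. Drop the McNemar test on overall adverse-event incidence. Report treatment-period incidence with exact 95% confidence intervals, and events per patient-week for each period. State beside them that monitoring was closer on treatment: a rate per patient-week corrects for period length, not for the number of looks.
2. Limit any paired period comparison to assessments that are named in advance and matched.
   - *Laboratory grades:* use one pre-specified scheduled draw per visit, and only tests scheduled at both time points. Simply setting Weeks -10 and 0 against Weeks 6 and 10 is not matched: blood gas and ionized calcium are not scheduled at Week -10, and chemistry is drawn twice in Weeks 6 and 10.
   - *Elicited events:* state the recall interval for each review. Do not count events reported at Week -10 as lead-in events, because that is the intake visit.
3. For severity, define the worst grade per patient per period, with no event scored 0. Make the signed-rank test, already the plan's fallback, the stated method.

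This needs only wording in Section 8.1, with no new visits, patients or data. The downside is one fewer p-value.

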The validity of the calcinosis assessment tool (CAT) will be assessed by focusing on the similarity between the CAT and other disease activity measures, like the Global Physician Score (GPhS) and Patient Reported Outcomes Measurement Information System (PROMIS®). Large disagreement between the CAT and other disease activity measures would suggest that the CAT tool is not measuring improvement in calcinosis but small differences may indicate that the CAT is capturing improvement in calcinosis that the other measures are not capturing. To assess the similarity between the disease activity measures, the Spearman rank correlation coefficient between the change in the CAT responses and the change in the other disease activity measure responses will be calculated. One can then test whether this correlation coefficient is different than zero, which would suggest an association between the two measures. A kappa statistic will be calculated to assess the agreement between discrete measures in the CAT and other discrete measures of disease activity. In the case where the number of categories observed by the CAT and other discrete measures of numbers of categories differ, the comparison will be accomplished by comparing the pooled scores for all categories of

**Abbreviated Title:** Sodium Thiosulfate (STIC)

**Version Date:** July 07, 2023

the CAT to the pooled scores of each independent finding using a nonparametric Wilcoxon ranked sum statistic. Evaluation of the Mawdsley Calcinosis Questionnaire will be performed in the same manner as for the CAT. A cluster analysis will be considered to explore how well the change in VAS, along with other measures of disease activity, such as change in Global Physician Score, Patient Reported Outcomes Measurement Information System, MRI, CT scans, DEXA scans and vascular imaging, can distinguish between responders to intravenous sodium thiosulfate therapy and non-responders. Responders will be defined as those individuals who meet the primary end point and non-responders will be those individuals who fail to meet the primary end point. A Spearman rank correlation coefficient will be used to identify disease activity measures that are highly correlated and contain the duplicate information. This will aid in variable selection for future multivariate analyses to identify responders to therapy. We will also attempt to assess the responsiveness of these tools through their standardized response means.

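### Fisher's exact test is the only hypothesis test named for responder versus non-responder comparisons, yet the comparison named in Section 2.1 is of gene and protein expression, which is quantitative

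*Combined protocol and SAP*

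**What the plan says.** Section 8.1 (Statistical Analyses): "Fisher exact tests will be used to test for differences between responders and non-responders to therapy". The sentence names no variables and no cut points. It follows a sentence assigning McNemar tests to categorical measures. The next sentence deals with adverse event severity and quantitative measures: "quantitative measures of improvement in calcinosis lesions and myositis activity will be analyzed using paired t-test or regression to control for additional covariates".

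Section 2.1 (Outcome Measures) lists gene expression, assessed on RNA and protein, as a secondary outcome. The purposes it gives as examples are treatment-related change "or differences between responders and non-responders to therapy".

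The rest of 8.1 that bears on the point:
- Gene expression changes associated with therapy are analysed by paired t-tests with false discovery rate control. That is a within-patient comparison.
- If normality cannot be achieved, "analogous nonparametric tests, such as the Wilcoxon Signed Rank test, will be used in the analysis". The example given is a paired test.
- A Wilcoxon rank-sum statistic appears, but for comparing categories of the Calcinosis Assessment Tool with other discrete measures.
- A cluster analysis may be considered, to explore how well change in VAS and other activity and imaging measures "can distinguish between responders to intravenous sodium thiosulfate therapy and non-responders".
- On who counts as a responder, the section gives only this: "Responders will be defined as those individuals who meet the primary end point"; no individual threshold is attached.

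**The concern.** Expression levels, and most of the other measures a responder analysis would draw on (VAS, PROMIS, imaging quantities), are continuous or nearly so. Fisher's exact test works on counts in categories. If the 8.1 sentence is followed for the comparison named in 2.1, each quantitative measure must first be cut. Two things are then at stake.

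First, power. The groups come from about 13 patients, and cutting gives away information they can ill spare.

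Second, reproducibility. With no cut point fixed in advance, the choice is made after the data are seen, and in samples this small moving one patient across the cut can carry a result over 0.05. For expression data the planned false discovery rate control sets a stricter per-gene threshold, so lost power costs more.

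**Working it through.** **The plan's own figure.** The documents state no power for the responder comparison. They state N = 13 for the primary paired t-test (Section 8.2: mean difference 10 mm, SD 10 mm, two-sided 0.05, 90% power). With noncentrality (10/10)·√N and N − 1 degrees of freedom, power is 91.1% at N = 13 and 88.3% at N = 12, so 13 reproduces. Allowing for 25% dropout, 13/0.75 = 17.3, rounded up to 18, also as stated (Section 8.3). The number of completers is therefore sound as an input.

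**Assumptions not in the documents.** Normal data with equal SDs; true difference d = 1.5 SD, responders higher; responder/non-responder splits of 7/6, 8/5, 9/4 and 10/3; two-sided 0.05 without multiplicity adjustment.

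**Methods.**
- Two-sample t-test: noncentral t with 11 degrees of freedom, critical value 2.201, noncentrality d/√(1/n₁ + 1/n₂). For 8/5: 1.5/√(1/8 + 1/5) = 2.63, power 67%.
- Exact rank-sum: simulation, 6,000 runs.
- Fisher, midpoint cut: the cut lies halfway between the group means. The chance of lying above it is Φ(0.75) = 0.773 for responders and 0.227 for non-responders. Power is the summed binomial probability of all tables with p ≤ 0.05.
- Fisher, median split: simulation. With 13 patients one patient is the median and must go to one side, so both placements are shown.

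| Split | t-test | Rank-sum | Fisher, midpoint cut | Fisher, median patient low | Fisher, median patient high |
|---|---|---|---|---|---|
| 7/6 | 69% | 60% | 41% | 27% | 56% |
| 8/5 | 67% | 62% | 41% | 44% | 28% |
| 9/4 | 62% | 51% | 28% | 0% | 46% |
| 10/3 | 55% | 51% | 31% | 0% | 0% |

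Simulated entries carry an error of about one percentage point.

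**Why zeros occur.** There are C(13,6) = 1,716 ways to choose which six patients fall in the smaller half.
- 9/4, perfect separation, median patient low: the table is [[6,3],[0,4]]. Two-sided p = (84 + 36)/1,716 = 0.070.
- 9/4, same data, median patient high: the table is [[7,2],[0,4]]. p = 36/1,716 = 0.021.
- 10/3, best case: p = 120/1,716 = 0.070. A median-split Fisher test cannot reach 0.05 with this split, whatever the data.

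**Information lost at the midpoint cut.** The table compares d needed for 80% power; the loss is 1 minus the squared ratio.

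| Split | t-test | Fisher | Loss |
|---|---|---|---|
| 7/6 | 1.71 | 2.35 | 1 − (1.71/2.35)² ≈ 47% |
| 9/4 | 1.85 | 2.77 | 1 − (1.85/2.77)² ≈ 55% |
| 10/3 | 2.03 | 2.68 | 1 − (2.03/2.68)² ≈ 43% |

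The large-sample loss for a median split is 1 − 2/π = 36%.

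**The case against.** The strongest reply is that the plan nowhere says quantitative data will be dichotomised. The Fisher sentence names no variable and sits directly after the sentence on categorical measures, so it may be meant as the between-group counterpart of McNemar. That reading is fair, and on it nothing is discarded. It does not close the gap, because the expression comparison in 2.1 is then left without a named test: the paired tests are within-patient, and the regression is not linked to responder status. Either reading calls for the same edit.

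A reader might also infer that Fisher is the only method of any kind offered. It is not: 8.1 allows for a cluster analysis on mainly quantitative measures, with no need for cut points. That analysis is only to be considered, and no test, estimate or interval is attached to it, so Fisher remains the only hypothesis test named.

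A reader might infer that most of the information would be thrown away. The figures support roughly half at a well-placed cut; only the 9/4 split goes above half. The median split is an illustration, not something the plan proposes.

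Finally, a reader might take this to undermine a stated secondary aim. The secondary objectives in Section 2 do not list explaining who responds. Section 2.1 mentions it once, as an example within the gene expression outcome. With about 13 patients it is hypothesis-generating under any test, and false discovery rate control would lower per-gene power for every method in the table.

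**Conclusion.** The point holds in limited form. Section 8.1 names one hypothesis test for responder differences, and that test does not suit the quantitative comparison Section 2.1 names unless cut points are defined, which they are not. Under the assumed splits and a 1.5 SD difference, applying Fisher to cut data costs about 24 to 34 percentage points of power against the t-test at a midpoint cut (10/3: 55 − 31 = 24; 9/4: 62 − 28 = 34). With a median split the result can turn on the placement of one patient. These sizes rest on splits, an effect size and normality that the documents do not supply. They show the direction and rough scale of the loss; they do not predict this trial's power. The primary analysis and the sample size are untouched. The change is worth making because it is cheap and fixes the method before the data are seen.

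**What to change.** Replace the Fisher sentence in 8.1 with wording to this effect: responders and non-responders will be compared on quantitative measures by two-sample t-test (moderated for gene expression, with the false discovery rate control already planned) or by exact Wilcoxon rank-sum test, reporting the estimated difference and 95% CI; Fisher exact tests will be used for categorical measures only.

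For the comparison to be carried out at all, 8.1 also needs an individual-level responder threshold. Responders are defined there by meeting the primary end point, which Section 8.2 describes as a mean difference across patients, so the two groups cannot be formed as written.

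The cost is a sentence or two in the analysis section. No new data, visits or patients are needed.
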